# **Protocol Development**

Protocol Amendments				
The following amendments and/or administrative changes have been made to this protocol since the implementation of the first approved version.				
Amendment number	Date of amendment	Protocol version number	Type of amendment	Summary of amendment

Funding and Support in Kind	
Funder	Financial and non-financial support given:
National Institute for Health Research (NIHR)	£1,782,916.15
Funding Scheme	Funder's reference number
NIHR Health Technology Assessment (HTA) Programme	NIHR130632

#### Funding Call

19/59 HTA Researcher-led call Primary Research

This study is funded by the NIHR HTA programme as referenced above. The funder had no role in the trial design. The views expressed are those of the authors and not necessarily those of the NIHR or the Department of Health and Social Care.

The funder will have no role in the data collection, trial management, data analysis or interpretation of data, or in the writing of the final report.

## **Compliance statement:**

This protocol describes the ERASER Trial only. The protocol should not be used as a guide for the treatment of participants not taking part in the ERASER Trial.

The trial will be conducted in compliance with the approved protocol, the Principles of Good Clinical Practice (GCP) as defined by the UK Policy Framework for Health and Social Care Research, Data Protection Act 2018 and the Mental Capacity Act 2005. Every care has been taken in the drafting of this protocol, but future amendments may be necessary, which will receive the required approvals prior to implementation.

# **Trial Summary**

Title	The ERASER Trial: Early Rib Analgesia with Serratus. A pragmatic randomised control trial evaluating the clinical and cost-effectiveness of serratus anterior plane block with catheter insertion compared to usual care in patients with multiple rib fractures.								
Acronym	ERASER								
Objectives	Primary objective To determine whether treating multiple rib fractures (MRF) patients with serratus anterior plane block (SAP) decreases the rates of pneumonia five days after randomisation, as defined by a blinded end point review committee, the clinical pulmonary infection score (CPIS) and all available trial related clinical information.								
	Secondary objectives								
	To determine whether treating patients with MRF with SAP:								
	
 
Reduces pain – this will be assessed through a numerical rating scale of 0-10, recorded every 4 hours, day 1 to 5, day 14 and before discharge, and by the patient-reported Brief Pain Index (BPI) at one and three months post-randomisation.
 
Improves ventilatory function - measured by incentive spirometry, peak expiratory flow twice a day via the daily assessment log until discharge
 
Reduces the number of days ventilated and the requirement for invasive/non-invasive methods
 
Improves 30-day mortality and 3-month mortality
 
Impacts opiate consumption such as morphine and related compounds
 
Reduces hospital re-admission within 30 days of discharge
 
Is cost-effective in the NHS setting assessed through a cost-utility analysis
 
Impacts Patient-Reported Outcome Measures (PROMs) at one and three months post-randomisation:         
 
EQ-5D-5L
 
Medical Research Council (MRC) dyspnoea scale (at 3 months only)
 
BPI
 
McGill Pain Questionnaire (SF-MPQ-2)
 
 
 
								
Trial Design	A pragmatic, multicentre, open-label, 1:1 two-arm allocation concealed randomised controlled trial with an internal pilot and complete economic evaluation.								
Target Population	Patients aged $\geq$ 16 years with unilateral or bilateral $\geq$ 3 MRF following blunt chest trauma that occurred $\leq$ 72 hours before hospital admission.								
Eligibility Criteria	
 
Inclusion criteria
 
Patients ≥16 years with unilateral or bilateral ≥3 rib fractures following blunt chest trauma
 
Traumatic injury that occurred ≤72 hours before hospital admission.
 
Exclusion criteria
 
Severe traumatic brain injury with a predicted ventilatory requirement >7 days
 
Acute quadriparesis
 
Spinal fracture precluding mobilisation
 
Penetrating trauma or open rib fractures
 
Upper airway injury requiring intubation and mechanical ventilation with an expected dependency of more than 5 days (e.g., tracheal disruption)
 
Any chest wall injuries that preclude a catheter insertion
 
								

	
 
Not anticipated to survive ≥48 hours
 
						
	
 
Contamination or infection at the site of potential SAP insertion
 
						
	
 
Any contraindication for the SAP block catheter insertion
 
						
	
 
Patients of childbearing age who have tested positive for pregnancy
 
						
Sample Size	824 participants						
Setting	Intensive Care Units and wards within NHS Major Trauma Centres in the United Kingdom with a track record of participating in critical care research and confirmed to have access to MRF patient populations.						
Intervention	SAP + usual care						
arm	SAP catheter inserted, under ultrasound guidance, in the lateral chest wall between latissimus dorsi and serratus anterior muscles in the midaxillary line. A local anaesthetic will be infused using a continuous infusion pump, according to local standard practice.						
	Usual care						
Control Arm							
	Usual NHS trauma care, which may consist of twice a day physiotherapy, multimodal analgesia, incentive spirometry when possible and rib fixation.						
Outcome	Primary outcome						
Measures	
 
New diagnosis of pneumonia, as agreed by a blinded end point assessment committee, five days after randomisation.
 
						
	Secondary outcomes						
	
 
Pain assessed using a numerical rating scale (0-10), recorded every 4 hours, day 1 to 5, day 14 and before discharge, and by the patient-reported BPI at one and three-months post-randomisation.
 
						
	
 
Ventilatory function measured by incentive spirometry and peak expiratory flow twice a day via the daily assessment log until discharge
 
						
	
 
Number of days ventilated and the requirement for invasive/non-invasive methods
 
						
	4 30 day and 3 month mortality						
	5. Complications and safety data associated with SAP						
	6. Opiate consumption such as morphine and related compounds						
	7. Length of stay in hospital and critical care level two/three facility						
	8. Hospital re-admission within 30 days of discharge						
	9. Patient-Reported Outcome Measures (PROMs) at 1 and 3 months:						
	• EQ-5D-5L						
	
 
Medical Research Council (MRC) dysphoea scale at 3 months only
 
						
	
 
Brief Pain Index (BPI)
 
						
	
 
McGill Pain Questionnaire (SF-MPQ-2)
 
						

<sup>1 The blinded end point review committee will make their diagnosis based CPIS and all available trial realted clinical information

# 1. BACKGROUND AND RATIONALE

# 1.1. BACKGROUND

## 1.1.1.Burden of the condition

Patients with Multiple Rib Fractures (MRF) contribute up to 10% of hospital admissions to Major Trauma Centres (MTC) in the UK (1). Often this leads to a significant risk of morbidity and mortality from initial thoracic injury or a consequence of secondary insults related to their rib fractures. The pain caused by MRF prevents patients from coughing and moving effectively, leaving them unable to clear secretions and increasing the risk of developing severe infections such as atelectasis, pneumonia, sepsis, and acute respiratory distress syndrome. Pneumonia is a complication of MRF and is diagnosed in 11-31% of MRF patients, increasing their mortality risk (2-4). These complications can delay the Intensive Care Unit (ICU) and hospital discharge and cause a long-term impact on mortality and morbidity. Conservatively, MRF cost approximately £7000 per patient in the acute setting (5) and long-term costs are substantially more because of the loss of societal productivity. Therefore, it remains a significant health and economic burden in the UK. 40% of these patients are of working age, and 60% do not return to full-time employment for five years.

## 1.1.2. Current Practice and existing research

Analgesia has been shown to reduce the risk of respiratory complications by enabling deep breathing, cough, and early mobilisation [6, 7, 8]. Regional analgesia with paravertebral catheters (PA) or thoracic epidural (TEA) was considered the 'gold standard' for the management of pain after MRF (9). A national survey conducted by the Chief Investigator (CI) and team demonstrated that the use of regional anaesthesia was limited due to patient factors, associated injuries, and availability of local expertise, with only 18% having access to these regional anaesthetic techniques (2-4). Opiate based pain relief is the current usual care despite its adverse effects like delirium, cough, and respiratory suppression (2-4, 6, 7). Respondents highlighted that the pain was never 'always' controlled. From the survey, it was found that clinicians preferred regional techniques, but barriers to the insertion of PA and TEA prevented their widespread use. The main obstacles were contraindications (69%), skill mix (64%), service and time pressures (52%), and inability to position patients appropriately (48%).

## 1.2. TRIAL RATIONALE

Patients with MRF require a simple, safe, effective, and universally available analgesic option. Serratus Anterior Plane Block (SAP) is a new technique placed under ultrasound guidance where the catheter is inserted in the lateral chest wall between latissimus dorsi and serratus anterior muscles in the midaxillary line. It blocks the pain caused by MRF and has the potential to provide a simple, easy, safe, and effective analgesic delivery technique in most patients for up to 10 days (10).

The CI, along with collaborators, conducted a cross-sectional cohort study on SAP. Using the Trauma Audit and Research Network database, 203 patients admitted to two Major Trauma Centres with MRF who received regional analgesia between 2016-2018 were included in the study (11). The primary outcome was a change in pain scores (0=no pain, 1=mild pain, 2=moderate pain, 3=severe pain) and inspiratory volumes (ml) pre- and post-regional analgesia. SAP Catheter, PA Catheter and TEA Epidural were assessed. The results showed an improvement in inspiratory volumes and a reduction in pain scores across all groups. Inspiratory volumes in the SAP group increased from (mean  $\pm$  standard deviation (SD)) 959 mls  $\pm$ 726 to 1667 mls  $\pm$  713 mls (p<0.001). Pain scores with SAP block significantly

reduced from moderate/severe to mild/moderate  $2.42 \pm 0.96$  to  $1.14 \pm 0.81$  (p<0.01). A similar increase in inspiratory volumes and reduction in pain scores was observed with PA and TEA, but with no statistically significant difference between the groups. These results suggest that post block SAP analgesia improves inspiratory volumes and reduces pain scores similar to PA or TEA. SAP catheters have the potential to radically increase the accessibility of regional analgesia to patients with MRF, similar to the impact of fascia iliac blocks for hip fracture pain. International societies have advocated that a high-quality prospective trial is urgently needed (12). The proposed pragmatic multicentre randomised controlled trial (RCT) comparing SAP to usual care would provide conclusive evidence to address clinicians' moral and ethical dilemmas during pain management after MRF.

An internal literature review performed by our group on the efficacy of SAP analgesia found that there were no published prospective RCTs for SAP analgesia in thoracic trauma (11). A narrative review of the case reports case series and retrospective reviews suggest a significant improvement in pain scores and inspiratory volumes following SAP analgesia, as indicated by our cross-sectional cohort study data (13-15). A second systematic review on the safety of SAP analgesia with the terminology broadened to include postoperative surgical patients returned 6 RCTs that reported no adverse events after SAP analgesia. At the time of review (2022), there were 3 RCTs registered with clinicaltrials.gov (16-18), but their methodology is significantly different to the ERASER Trial. The participants in this trial will better represent the trauma cohort in the UK, with a robust methodology and sufficient power to detect clinically relevant patient-centred outcomes. This pragmatic, multicentre RCT with a stratified approach will ensure the generalisability of results to trauma practice worldwide.

The ERASER Trial aims to answer a vital question for both patients and clinicians with the prospect of improving patient comfort, care and outcome, and costs in the NHS. The results of this study will have a significant impact in 2 different ways:

**Patient benefit:** if the trial finds that either treatment protocols reduce acute pain and pneumonia, maintains patient safety, and is cost-effective, it will significantly impact the way patients with MRF in the NHS are currently managed.

**Change in practice**: if SAP is effective, it will lead to a consensus on the preferred usual care for patients with MRF and prompt rapid change to NICE guidance, with the consequential amendment to care pathways and resource use across the NHS. However, importantly if there were no benefit, the trial would provide evidence to stop the use of the ineffective treatment within the NHS.

## 1.2.1.Justification for participant population

The patients involved in the ERASER Trial will be adult patients (aged  $\geq$ 16 years) with three or more unilateral or bilateral fractures following blunt chest trauma and admission to the hospital. This patient cohort was selected as they are at high risk of developing post-traumatic complications, including pneumonia.

#### 1.2.2. Justification for design

ERASER is a randomised controlled trial. The insertion of regional anaesthetic catheters and continuous infusions of local anaesthesia cannot be blinded for apparent reasons. This was discussed with the focus group and the multidisciplinary trial team, who agreed to the trial design.

## 1.2.3.Choice of intervention

In the CI's cross-sectional cohort study (11), SAP block provides comparable, adequate, and effective analgesia to epidural analgesia post-insertion. A 3-arm trial was considered comparing SAP against TEA/PA and opiates individually; however, the group decided against this because exclusively comparing SAP to TEA/PA would significantly reduce recruitment due to restrictions on TEA/PA

insertion due to coagulopathy, head and spinal injuries, comorbidities and use of anticoagulant medications. The current trial will allow better recruitment due to less stringent inclusion/exclusion criteria making the results more applicable and generalisable. This approach also optimises the chance that significant differences in pneumonia rates, mortality and length of stay are identified as the patients with the highest levels of injury and comorbid disease who may benefit most from SAP analgesia are not excluded (19, 20).

#### 1.2.4. Justification of choice of the primary outcome

The Clinical Pulmonary Infection Score (CPIS) is pragmatic, commonly used and provides an easy and reproducible measure of hospital-acquired pneumonia (HAP) (it includes fever, leucocytosis, oxygenation, tracheal secretions, and chest radiograph to diagnose pneumonia). HAP is associated with longer hospital stays, ventilatory support and organ failure. This primary outcome was discussed and accepted as the most relevant clinical outcome in the national survey, Patient and Public Involvement (PPI) meetings, and international rib fracture pain management conference held at Geisingen, Germany (July 2019).

# 2. AIMS AND OBJECTIVES

The trial aims to evaluate the clinical and cost-effectiveness of SAP with usual care compared with usual care only in adult patients with MRF admitted to the hospital.

#### 2.1. INTERNAL PILOT

There will be a 12-month internal pilot. The aims of the pilot are to assess whether the recruitment rate, randomisation and adherence to the follow-up assessment schedule are feasible. it will:

- Involve sites that receive between 200-300 patients with significant chest injuries (≥3 rib fractures/flail segments) per year
- Recruit 100 patients within 9 months (12% of the total sample) based on an anticipated recruitment rate of 4 patients, per centre, per month

In terms of recruitment, the success of the internal pilot will be based on the traffic light system.

Go: 100% recruitment: progress to the main trial.

Amend: 50-99% recruitment: continuation of recruitment is contingent on the submission (and approval by the funder) of a clear rescue plan.

**Stop:** <50% recruitment: stop the trial.

Randomisation, adherence to the follow-up schedule and any unforeseen issues, will be reviewed prior to progressing to the main trial, and, if required, amendments to the protocol will be made accordingly.

#### 2.2. MAIN TRIAL OBJECTIVES

#### 2.2.1.Primary objective

To determine whether treating MRF patients with SAP decreases the rates of pneumonia 5 days after randomisation, as defined by a blinded end point review committee using CPIS and all available trial related clinical information.

#### 2.2.2.Secondary objectives

To determine whether treating MRF patients with SAP:

- Reduces pain using a numerical rating scale (0-10), recorded every 4 hours on day 1 to day 5, day 14 and discharge. Pain will also be assessed through use of the patient-reported Brief Pain Index (BPI) at one and three months post-randomisation.
- 2. Improves ventilatory function measured by incentive spirometry, peak expiratory flow twice a day via the daily assessment log until discharge
- 3. Reduces the number of days ventilated and the requirement for invasive/non-invasive methods
- 4. Improves 30 day and 3-month mortality
- 5. Is safe and not associated with significant complications
- 6. Impacts opiate consumption such as morphine and related compounds
- 7. Reduces hospital re-admission within 30 days of discharge
- 8. Is cost-effective in the NHS setting, this will be assessed through a cost-utility analysis
- 9. Impacts Patient-Reported Outcome Measures (PROMs) at one- and three-months post randomisation:
  - o EQ-5D-5L
  - Medical Research Council (MRC) dyspnoea scale (at 3 months)

o BPI

• McGill Pain Questionnaire (MPQ)

# 3. TRIAL DESIGN AND SETTING

## 3.1. TRIAL DESIGN

A pragmatic, multicentre, open-label, 1:1 two-arm allocation concealed RCT with an internal pilot and full economic evaluation.

## 3.2. TRIAL SETTING

The trial will take place both on wards and ICUs of NHS MTCs in the UK with a track record of participating in critical care research and confirmed access to the MRF patient population.

The pilot trial will consist of several MTC's in the UK that has a high number of trauma patients with  $\geq$ 3 MRF. On successful completion of the pilot, further sites will be opened for the main trial.

## 3.3. ASSESSMENT OF RISK

All clinical trials can be considered to involve an element of risk, and in accordance with the Birmingham Clinical Trials Unit (BCTU) standard operating procedures (SOP), this trial has been risk assessed to clarify any risks relating uniquely to this trial beyond that associated with usual care.

ERASER is a non-CTIMP that has been formally risk assessed by BCTU as 'low risk with no higher than the risk of usual care in this setting' on the basis that both the intervention and control arms are already in common usage throughout the UK and the safety profiles are well established.

The assessment and management of risks is detailed in the trial Risk Assessment document. A review of risk will be conducted in accordance with BCTU SOPs throughout the trial.

# 4. ELIGIBILITY

## 4.1. INCLUSION CRITERIA

The site PI will be a medically qualified doctor or an appropriately qualified health care professional and will be responsible for maintaining oversight of the confirmation of the eligibility process. In order to be eligible for the ERASER trial, patients must meet the following inclusion criteria:

- 1. Aged ≥16 years with unilateral or bilateral ≥3 rib fractures following blunt chest trauma
- 2. The injury occurred ≤72 hours before hospital admission

#### 4.2. EXCLUSION CRITERIA

If any of the following exclusion criteria apply, the patient is not eligible to be randomised into the ERASER trial:

- 1. Severe traumatic brain injury with a predicted ventilatory requirement >7 days
- 2. Acute quadriparesis
- 3. Spinal fracture precluding mobilisation
- 4. Penetrating trauma or open rib fractures
- 5. Upper airway injury requiring intubation and mechanical ventilation with an expected dependency of more than 5 days (*e.g., tracheal disruption*)
- 6. Any chest wall injuries that preclude a catheter insertion
- 7. Not anticipated to survive  $\geq$ 48 hours
- 8. Contamination or infection at the site of potential SAP insertion as deemed by the local PI
- 9. Any contraindication for SAP block catheter insertion as deemed by the local PI
- 10. Patients of childbearing age who have tested positive for pregnancy

<sup>1 Pregnancy test taken as part of usual care

## 4.3. CO-ENROLMENT

Due to the emergency nature of this trial, the research team at the site is highly unlikely to be aware if a participant is already participating in a clinical trial. Where a participant is subsequently found to have been participating in a concurrent trial, the site should inform the ERASER Trial Office, who will in turn request that the CI assesses any safety concern or impact on the trial data. The site should follow its local procedure for reporting trial co-enrolment.

Where appropriate, participants in this trial may take part in other observational and selected interventional studies. Co-enrolment will be considered on a case-by-case basis after discussion with the Trial Management Group (TMG) which will take into account statistical considerations and potential impacts on primary and secondary outcomes. The site should contact the ERASER Trial Office should such queries occur to seek advice prior to enrolling the participant.

# 5. CONSENT

Potential participants with MRF will, by default, be critically ill due to the effects of sedation, possible infection and possible delirium and, therefore, may lack the capacity to consent for themselves. Sites should follow the appropriate consent procedure depending on the potential participant's mental status. Where the potential participant lacks the capacity to consent for themselves, advice will be sought from a consultee (for sites in England and Wales; see section 5.1.2) or consent will be sought from a legal representative (for sites in Scotland; see section 5.1.5. Contact with the potential participant, consultee, or legal representative, to initiate the consent process should be made as soon as practically possible after the initial emergency has passed, taking the utmost care and sensitivity in doing so.

The Principal Investigator (PI) or delegate(s) are responsible for obtaining written informed consent for each participant and/or advice from a consultee or consent from a legal representative. Consent may also be taken by other members of staff at the site (e.g. Research Nurse or Allied Health Professionals) if local practice allows, and this role has been delegated by the PI on the Site Signature and Delegation Log.

Given the urgent nature of the condition, randomisation and intervention should occur on the same or next working day after consent has been taken.

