## 6.2. RANDOMISATION

## 6.2.1.Randomisation System

Randomisation will be provided by a secure online randomisation system at the BCTU (available at https://bctu-redcap.bham.ac.uk), thereby ensuring allocation concealment. Unique log-in usernames and passwords will be provided to site staff that have been delegated the role of randomising patients into the trial as detailed on the trial Site Signature and Delegation Log. These unique log-in details must not be shared with other staff and in no circumstances should staff at sites access the system using another person's login details. The online randomisation system will be available 24 hours a day, 7 days a week, apart from very short periods of scheduled maintenance. If delegated site staff have lost their username or password, the ERASER Trial Office should be contacted directly via email or telephone using the contact details outlined on page 5 of the protocol. In rare instances that the database is unavailable, researchers can call the telephone toll-free randomisation service ([name]) Monday to Friday, 09:00 to 17:00 UK time, except for bank holidays, government guided closures and University of Birmingham closed days.

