# 7. TRIAL INTERVENTION

#### 7.1. TRIAL INTERVENTION

Participants randomised to the control arm of the ERASER trial will receive the usual care for analgesic management for patients with MRF as per local standard practice. Whereas patients randomised to the intervention arm will receive SAP plus usual. In order to be adherent to the intervention arm of the trial, the SAP catheter has to be inserted for a **minimum of 24 hours**, if the catheter is removed prior to this, it should be classified as a failure of intervention and a change of status form should be completed accordingly. There is no trial mandated maximum duration for how long a SAP catheter should remain in place, both monitoring and removal should be in line with local standard practice.

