#### 8.2. MAIN TRIAL OUTCOMES

#### 8.2.1. Primary Outcome

New diagnosis of pneumonia, as agreed by a blinded end point assessment committee, 5 days after randomisation.

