#### 9.1.2.Baseline (Day 0: within 48 hours of randomisation)

Once consent has been obtained, the following will be recorded prior to randomisation and participant receiving the allocated intervention:

- Relevant medical history (pre-admission details; treatments given to fractures prior to hospital admission)
- Charleson Comorbidity Index
- Basic demographic data
- Details of injury
- Current medication (concomitant medication; analgesic medication; other medication/treatments)
- Routine Assessments:
  - Injury severity scores (Abbreviated injury scale (AIS), frailty score, CPIS, Sequential organ failure assessment (SOFA))
  - ICU and/or hospital admission status
  - Mechanism of injury (pulmonary contusion, anatomical location of fracture, presence of flail segment) and details of other injuries on body
  - Overview of analgesic and other medication
  - Body temperature at hospital
  - Lung function assessments including FEV1 and FVC
  - Chest x-ray (CXR) interpretations, if any (new or progressive infiltrate characteristic of pneumonia or a new consolidation)
  - Tracheal secretions
  - Oxygenation
  - A pregnancy test will be carried out on patients of childbearing potential age, as per usual care
  - o CPIS
  - Covid-19 diagnosis and treatment
- Routine laboratory tests: (WBC; white cell count, CRP; C-reactive Protein; culture of tracheal aspirate)
- EQ-5D-5L
- Rating of pain (VAS)
- Blood samples (see section 9.1.5)

The participant will be randomised, and the allocated intervention will begin. The site research team will start to monitor and record any AEs and SAEs as described in section 10.

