#### 9.1.3. During hospital stay (Day 1 (from time of randomisation) until discharge from hospital)

The following data will be collected **daily** from the time of randomisation, in line with the routine collection of usual care data:

- Current medication (concomitant medication; analgesic medication; other medication/treatments)
- Lung function assessments.
- FEV1 and FVC to be collected twice per day
- Rating of pain (VAS) every 4 hours on day 1-5, then on day 14 and at discharge
- Body temperature
- SOFA
- CPIS Day 5 only
- CXR interpretations
- Tracheal secretion
- Oxygenation
- Rating of pain (VAS) every 4 hours on day 1-5, then on day 14 and at discharge
- Critical care minimal data set
- Intervention insertion date/time (only recorded on the date of insertion)
- Intervention removal date/time (only recorded on the date of removal)
- Failure of intervention (i.e. SAP Catheter could not be inserted or removed within 24 hours)
- Routine laboratory tests: (WBC, CRP, culture of tracheal aspirate)
- ICU and/or hospital admission status
- Organ dysfunction through use of the SOFA score
- Other medications or treatments required for MRF
- Adverse events
- Survival status
- Blood samples (see section 9.1.5)

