#### 9.1.5.Blood sampling for future research

In anticipation of future studies, blood will be collected and spun from participants who have provided consent (either for themselves or where consent/ an opinion has been sought from a legal representative or consultee). These samples will be taken within 24 hours of randomisation, day 5 ( $\pm$  24h) and day 14 ( $\pm$ 24h) if the participant is still admitted and at discharge. The blood sample should be stored at -80°C, and eventually shipped in batches to the laboratory at the University of Birmingham. Full instruction of sample preparation and shipment will be available in a separate Work Instruction.

	Screening	Baseline	Days during hospital			ital	At discharge	Months post- Randomisation	
Visit	-	Day 0	1-5	6-13	14	15+	-	1	3
Time window	$\leq$ 72 hours	$\leq$ 48 hours		Dail	у		± 6 hours from discharge	± 7 d	ays
Eligibility check	х								
Valid informed consent		х							
Relevant medical history		х							
Basic demographic data		х							
Charleson Comorbidity Index		х						Х	х
Current medication		х	х	х	х	х	Х	Х	х
Date & time of injury		х							
Covid-19 diagnosis and treatment		х							
ICU/Ward admission details		х	x	х	x	x	x		
Randomisation		х							
Intervention insertion			х						
Intervention removal			х	х	х	х			
Failure of Intervention		х							
Date of discharge							Х		
Routine physical exam:									
Pregnancy test		х							
Body temperature		х	х	х	х	х			
AIS		х							
Frailty score		х							
SOFA		х	х	х	х	х			
CPIS		х	х	х	х	х			

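### No limit is set between randomisation and block insertion, so a randomisation before a weekend can use up days of the five-day primary outcome window while both arms have usual care only

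*Protocol*

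**What the plan says.** Section 5 holds the only timing rule: "randomisation and intervention should occur on the same or next working day after consent has been taken". It starts at consent, is counted in working days, and covers randomisation and intervention together.

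The primary objective (2.2.1) asks whether SAP "decreases the rates of pneumonia 5 days after randomisation", and the primary outcome (8.2.1) uses the same starting point. Section 6.2.1 states: "The online randomisation system will be available 24 hours a day, 7 days a week".

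Three other places touch on the start of treatment:

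- Section 9.1.2: "The participant will be randomised, and the allocated intervention will begin". This gives an order, with no time limit.
- Table 1 has a row "Intervention insertion", marked in the column for Days 1-5. Section 9.1.3 has the insertion date and time recorded on the day it happens.
- Section 7.1: "In order to be adherent to the intervention arm of the trial, the SAP catheter has to be inserted for a" minimum of 24 hours. This concerns how long the catheter stays in. Section 9.1.3 describes failure of intervention in words that can be read as a 24-hour limit on removal only, or on insertion as well.

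Until the catheter is in, the intervention arm has usual care only, as the control arm does (7.1). Section 14.2 analyses participants as randomised, whatever their adherence.

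**The concern.** The treatment rule and the outcome clock start at different points and use different units. The rule runs from consent in working days; the outcome runs from randomisation in calendar days. A site that consents and randomises on Friday and inserts the block on Monday has kept to section 5, and 3 of the 5 outcome days have passed before the arms differ.

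Pneumonia that arises in that interval cannot be prevented by SAP but still counts in the SAP arm. The estimated effect therefore moves towards no difference. A wait of the same length before randomisation would not have this effect, because neither arm's clock would have started.

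This matters more because section 1.2 says a finding of no benefit would be evidence to stop using SAP in the NHS. Contrast lost in this way cannot be recovered in the analysis once patients have been randomised.

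**Working it through.** **Inputs from the protocol.** Section 14.1: control risk 15%, SAP risk 7.5%, two-sided 5%, 90% power, 371 per arm, 742 in total, 824 after 10% loss. Sections 2.2.1 and 8.2.1: a five-day window from randomisation.

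**Step 1: the plan's own figure.** With pooled variance under the null and no continuity correction,

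n = [1.960·√(2p̄(1−p̄)) + 1.282·√(p₁(1−p₁)+p₂(1−p₂))]² / (p₁−p₂)²

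Here p̄ = 0.1125. The bracket is 1.960·√0.1997 + 1.282·√0.1969 = 0.876 + 0.569 = 1.445, so n = 1.445²/0.075² ≈ 371 per arm. Power at 371 is 90.0%. Then 742/0.9 = 824.4, which agrees with 824. The stated size reproduces.

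**Step 2: longest lag the wording allows**, taking randomisation on the day of consent and insertion on the next working day:

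| Randomised | Inserted | Days lost | Share of window |
|---|---|---|---|
| Mon-Thu, Sun | next day | 1 | 20% |
| Sat | Mon | 2 | 40% |
| Fri | Mon | 3 | 60% |
| Fri, Monday holiday | Tue | 4 | 80% |
| Thu, four-day holiday weekend | Tue | 5 | 100% |

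**Step 3: dilution.** These assumptions are not in the documents: risk is even over the 5 days, SAP has no effect before insertion, and the relative risk is 0.5 from insertion on. With mean lag m days across the SAP arm,

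p₂ = 0.15 × (0.5 + 0.5 × m/5)

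A single patient who waits 3 days has risk 0.15 × (0.5 + 0.3) = 12.0%, a relative risk of 0.80.

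**Step 4: power at 371 per arm.** The shares delayed are also assumptions. The weekday scenarios take recruitment as even over the seven days.

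| Scenario | m (days) | SAP risk | RR | Power | Per arm for 90% |
|---|---|---|---|---|---|
| 5% of patients wait 3 days | 0.05×3 = 0.15 | 7.7% | 0.515 | 87.9% | 398 |
| All Friday patients wait 3 days | 3/7 = 0.43 | 8.1% | 0.543 | 83.3% | 456 |
| No weekend insertions (Fri 3, Sat 2, Sun 1) | 6/7 = 0.86 | 8.8% | 0.586 | 74.5% | 569 |
| Everyone at the longest ordinary-week lag | 10/7 = 1.43 | 9.6% | 0.643 | 60.3% | 789 |

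The last row is a bound: it needs Monday-to-Thursday patients to wait the full permitted day as well. The holiday lags of 4 and 5 days are not in any row.

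**The case against.** The strongest reply is that section 5 can be read the other way. It opens with urgency and treats randomisation and intervention as a pair, and section 9.1.2 puts one straight after the other. On that reading a Friday consent means both on Friday or both on Monday, and no outcome time is lost. The reading is natural, but the text does not require it, and nothing stops a site from splitting the pair. The verb is also a target and sets no limit.

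A reader might infer that sections 5 and 9.1.2 and Table 1 give three conflicting start times. They do not. Section 9.1.2 gives a sequence, Table 1 is a recording grid with Days 1-5 merged, and section 7.1 speaks only of duration. The fault is silence on the interval.

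A reader might also infer that a catheter inserted on day 5 plainly counts as adherent. Section 7.1 alone would allow that, but the failure wording in 9.1.3 may imply a 24-hour limit on insertion. Even so, a late block labelled a failure would stay in the intention-to-treat analysis on the same clock.

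The trial is pragmatic, so some delivery delay belongs to the effect being estimated. If the targeted halving already allows for it, the scenarios count it twice. This is a fair limit on the power figures. It does not explain why avoidable delay should fall after randomisation. Nor would a null result be beyond interpretation: insertion time and the randomisation record are both kept, so the lag can be described.

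**Conclusion.** The concern holds as a statement of what the wording permits. No section limits the time from randomisation to insertion, and on one permitted reading 3 of the 5 outcome days, or 4 to 5 over a bank-holiday weekend, can pass before treatment differs.

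The likely size is smaller than the worst case. Power would be about 88% to 75% in the scenarios confined to a small delayed share or to weekends, against a planned 90%. Two stronger conclusions are not supported: that the trial has 60% power, which needs every patient to be treated on the last permitted day, and that the sample size is wrong, since it reproduces exactly and merely makes no allowance for late insertion.

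All the diluted figures rest on the even hazard, an immediate full effect at insertion, and assumed shares delayed. Risk concentrated early in the window would make the loss larger, and risk concentrated late would make it smaller.

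**What to change.** - In sections 5 and 6.2.2, state that randomisation is performed when insertion can directly follow, so that any wait after consent falls before randomisation. One confirmation item on the randomisation form would support this.
- Report the distribution of time from randomisation to insertion in the SAP arm. The data are already collected.
- Reconcile sections 5, 7.1, 9.1.2, 9.1.3 and Table 1 on the interval between randomisation and insertion, and on what counts as failure of intervention. Which clinical rule applies is for the trial team to decide.

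The cost is wording and one form item. Some consented patients would be randomised later or lost before randomisation, which slows recruitment a little but does not bias the comparison. Section 9.1.2 and Table 1 give baseline a 48-hour window, so after a Friday-to-Monday wait some baseline items may have to be refreshed.
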